B.1 Screening, Baseline and 4 and 9 month Follow-up Research Assessment Procedures: Once the CG is identified (by self-referral, VA providers, or VINCI), indicates an interest in study participation, and consents (in-person or by phone), the RA will complete the initial screening and, if the CG is eligible, the baseline research assessment. Next, to ensure blinding of the RAs, the Project Coordinator will use a random number table to inform each CG of their group assignment. Procedures for the assigned study arm will commence (see B.2 and B.3). All CGs will be contacted again for 4- and 9-month follow-ups, at which point the majority of baseline assessments will be re-administered. Before each assessment, RAs will remind CGs not to disclose their assigned study arm. Data on care recipients' (CRs') health and service utilization will be extracted from the CRs' clinical record via VINCI, while CG VA and non-VA CG/CR health

and service utilization will be captured by CG assessment. All research assessments (including follow-ups) will be completed by the RA by telephone (with an email/mail-in option, if preferred) and include validated questionnaires regarding CR- and CG-level sociodemographic, clinical, work- related, and psychosocial variables (Appendix 1; Table 1). In-depth qualitative interviews will be conducted at 4-month follow-up with a subgroup of CGs (n=30) from the SOS arm.

These qualitative interviews will be audio recorded.

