B.3. UC Comparator Procedures: CGs in this arm will be contacted telephonically once by a CM. After a brief needs assessment, the CM will provide contact information for appropriate VA (e.g., local CSP clinicians) and non-VA community resources/services. CGs will be sent brochures for the national VA CSP. Information on both the program's website (which includes links to training, education, resources, and outreach programs for CGs) and the national CG hotline number will be included in the e/mailed packet. Receipt of information regarding the VA CSP is consistent with the standard of care for informal CGs in the VHA since 2010.³⁰ After this initial contact, CGs in this group will only be contacted again 4 and 9 months after baseline for administration of follow-up research assessments. CGs will be encouraged to seek medical, psychological, social support, and social services that are available to them through VAMCs or any other non-VA/community source. CGs in the SOS group will be offered similar information.

B.4. Training and Supervision: The SOS care CM will have 16 hours of training (telephone and webinar) that will cover the study protocols, modules, assessment tools, care documentation and performance standards. Training will continue during team supervision sessions (telephone

and webinar) and on an individual ad hoc basis (with Drs. [name], [name], and [name]).

Supervision sessions, held weekly, will involve review of specific cases.

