C.1. Measures and Data Collection Timeline: Table 1 (Appendix 1) describes the proposed assessment tools and timing. These data will be collected by the RAs. As part of SOS care, the CM will administer and document results from a brief C-WLQ every other session. For purposes of tracking the care process, the CM will document each contact with CGs, referrals to VA/community service agencies, and each contact with Veterans' PCPs/providers (when indicated) and results. Finally, in cases where CGs report needing assistance with the Veterans' care, CMs will track whether concerns were discussed with the Veterans' PCPs and whether recommendations were made or help was coordinated for scheduling in primary and specialty care. To complement the quantitative data analyses, we will use rapid qualitative content analysis to evaluate the intervention's acceptability, appropriateness, and value of the content from the CGs' perspective.

We propose to collect screening, baseline, intervention, and 4 and 9-month follow-up data in 42 months. Study enrollment will be on a rolling basis, and participation in the SOS intervention will occur over the span of 3-4 months. Research assessments will take up to 60 minutes by phone. Qualitative interviews with the subset of CGs will take up to 30 minutes. CGs will be paid \$40 for the baseline and \$25 for each follow-up research assessment (\$90); this is similar to the amount of compensation provided to participants in our other studies.⁴⁴ CGs completing qualitative interviews will get an additional \$10 at the 4-month follow-up.

4.3.2 Include a description of how anticipated risk will be minimized and include an analysis of risk vs. potential benefit.

There is minimal risk to CGs due to their participation in this study. There is also minimal risk to the Veterans whose medical records are accessed and extracted for recruitment and research purposes.

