In order to utilize Veterans' medical records for the purpose of identifying potentially eligible participants and recruitment, we are requesting a waiver of all elements of informed consent for Veterans, including HIPAA. We also are requesting a waiver of informed consent/HIPAA in order to extract Veterans' medical record data for research purposes. Without the waiver, we cannot verify the Veterans' diagnoses or extract and analyze clinical data, as only their CGs are consented and enrolled. Moreover, without access to Veterans' names, phone numbers, and addresses prior to their assent, we cannot contact potentially eligible participants for the initial screening and assent process.

We are also requesting a waiver of documentation of informed consent and HIPAA for study/intervention takes place primarily via phone and mail, we would like to obtain oral consent for the convenience of the CGs and to expedite the enrollment process. CG consent for participation in this study will be obtained either in person or over the phone. Informed consent procedures comply with current standards of the Institutional Review Boards at the CMCVAMC and VAWNYHS. After telephone discussion of the information in the consent form, and encouraging the asking of questions/concerns, the CG will be asked if s/he gives consent to enrolled in the study. The Research Coordinator/RA will be using an IRB approved script as well as a checklist to ensure each element of consent is covered. Interested CGs will be mailed a

copy of the verbal informed consent script. CGs also will receive a Copy of Notice of Privacy Practices, and acknowledgement of its receipt will be noted. In all cases, the investigators view the process of informed consent as an ongoing process that continues throughout participation in the study.
The electronic ICF data will be kept separate from any coded, de-identified data. Following the consent and baseline process, CGs will be randomized to either usual care or Caregiver SOS using a random number table.

6.2 Describe who will be obtaining informed consent, if applicable, and any circumstances that may need to be addressed (e.g. subjects with impaired decision making ability and the use of a legally authorized representative, etc.)

The Research Coordinator and Research Assistants (and, if needed, Care Manager) will be obtaining informed consent.

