6.3 If applicable, indicate how local site study personnel will be trained regarding human subjects' protections requirements and how to obtain and document informed consent.

All study personnel will complete and remain current on CITI and VA Human Subjects Training; PI and Research Coordinator will train staff on consent procedures.

7

Inclusion/Exclusion Criteria

7.1 Describe the criteria that determine who will be included in or excluded from the study.

Inclusion Criteria:

1. Veteran receives care at the Corporal Michael J. Crescenz VA Medical Center (CMCVAMC), VA Western New York Healthcare System (VAWNYHS), or affiliated community-based outpatient clinics
2. Veteran and CG are 18 years of age or older
3. Veteran and CG are community dwelling
4. Veteran has a confirmed diagnosis OR clinically significant symptoms of depressive disorder, generalized anxiety disorder, PTSD, and/or TBI (per medical chart).
5. CG is a relative or significant other who endorses that s/he assists the Veteran care recipient (CR) with two or more instrumental activities of daily living (IADLs). IADLs include: housework, managing finances, arranging/providing transportation (e.g., to medical appointments and community services), grocery shopping, preparing meals, health management and maintenance (e.g., giving medications, minimizing exposure and response to stress triggers), and arranging for and/or supervising the delivery of services for assistance with everyday activities.
6. CG is employed (i.e., works for pay ≥ 10 hours per week)
7. CG screens positive for at least mild-moderate distress (i.e., score ≥ 6 on the Kessler Psychological Distress 6-item Scale or a score ≥ 4 on the Kessler 6-item Scale and a score ≥ 2 on the Perceived Stress scale)
8. CG screens positive for at least moderate work role difficulty due to caregiving (i.e., $>3\%$ on the Caregiver Work Limitations Questionnaire)
9. CG is willing and able to provide informed consent.

Exclusion Criteria:

1. CG cognitive, hearing, visual, or other physical impairments leading to difficulty with informed consent process, assessment, or participation in intervention visits
2. CG unable to speak or read English

8. Study Evaluations

8.1. Describe all evaluations to be conducted (including screening; tests/questionnaires that will be administered; any procedures that subjects will be required to complete) and data collection methods. Include materials as an appendix or separate attachment.

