CMs also will enter clinical data into VA REDCap and the Behavioral Health Laboratory (BHL) software. The BHL software is a VA approved and network-wide installed software package that allows providers to track participants and to graphically display assessment reports. The software has been in use for more than 10 years in the VA. All REDCap and BHL data collection, transfer, and storage of data will be performed on the VA Intranet and thus access to the system is user based and requires maintenance of all relevant employee trainings. CR and CG- related VA and non-VA healthcare and service utilization will be obtained using VINCI or by self- report. When estimating non-VA utilization of care, we plan to follow HERC's guidebook which provides detailed documentation and suggestions for analyzing non-VA data on procedures.⁶⁸ The utilization database will include a "time window" variable spanning one year prior to and one year following the final CM call. Extracting clinical patient record data electronically to the greatest extent possible will improve validity and reduce respondent burden. Detailed procedures will be followed to protect against potential risks to privacy and breaches of confidentiality.

9. Data Analysis

9.1. Provide sample size determination and analysis (include anticipated rate of screen failures, study discontinuations, lost to follow-up etc.).

Power calculations were computed for Aim 1 based on 300 consenting CGs. Estimating a maximum of 20% attrition from follow-up (final n=120/group), typical correlation of .70 between baseline and each of two follow-ups, 5% significance tests, and 80% power, we will be able to find a minimum detectable effect size (MDES) of 0.235 standard deviations (SD). This is within the range of effect sizes found in other CG intervention studies.³⁷ For the primary outcome (Aim 1a) we expect a standard deviation for the K10 of about 10,⁵⁸ suggesting that we could detect a difference of 2.35 points between treatment and control based on mixed effects models. A clinically meaningful treatment-control difference of 3 points is well within the range of detectable differences. Similarly, for the secondary outcome measure (Aim 1b), a C-WLQ summary score improvement of lost productivity due to caregiving burden (SD=4.4%), will yield a MDES of 1.0%. Exploratory analyses will be underpowered.

9.2. Describe how, where and by whom the data will be analyzed.

All analyses will be run by the PI or Biostatistician.

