Power, Sample Size, and Missing Data: As described above, the MDES is 0.235 SD for 5% significance tests and 80% power with a starting sample of 300. Questionnaires will be administered by RAs using software that encourages response and does not permit multiple or out-of-range responses, for which missing data rates of 1-3% are typical and are easily resolved with multiple imputation techniques. While non-VA care will be assessed by self-report, VA claims databases are complete by design. We will conduct attrition analyses to assess differences in CG characteristics between those with complete vs. incomplete data. If differences are found, covariates will be included in final adjusted models. We acknowledge that we may be underpowered to address sample heterogeneity and moderators of treatment effect. Thus, to maximize the interpretability and utility of our findings, in addition to the models described below, the central tendency, variation and potential trends over time will be evaluated using means, standard deviations, and 75%, 85%, and 95% confidence intervals (CIs) plotted across time for each condition.⁷⁶ CIs will be interpreted with respect to clinically meaningful treatment group differences. Results from qualitative analyses also will be used to provide a context for treatment effects across potential moderators.

Preliminary Analyses: We will continually assess data quality and randomization success, testing for baseline group differences in key variables (e.g., gender, age, race/ethnicity, job flexibility, K10 and C-WLQ scores, and CR condition). If early analyses indicate group

differences, we will include the variables as covariates in the final adjusted models. We will review summary statistics (e.g., percentages, means and medians) to evaluate whether responses on the major variables (e.g., K10 distress score) are consistent with distributions obtained in other studies and psychometric performance is maintained (e.g., Cronbach's alpha statistics). We will apply appropriate transformations to highly skewed continuous variables. All preliminary analyses will be conducted using SAS version 9.3 (SAS Institute, Cary, NC).

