Specific Aims 1 and 2-Assessing Randomization Group Differences in Outcomes: In order to analyze the degree to which randomization group is associated with changes in our primary (CG distress) and secondary (CG work functioning) outcomes over time (Hyp 1a and 1b), we will run separate intent-to-treat, mixed effects linear regression models (using SAS PROC MIXED). Mixed models account for multiple observations (baseline and follow-up) and make use of all available data for each CG (regardless of drop-out or missing assessment periods). Specifically, we will specify a mixed effects model $Y_t = \beta_1 T + \beta_2 Z + \beta_3 TF + \beta_4 t + \epsilon$, where T is the indicator for treatment group (1 for SOS and 0 for UC), $t=0, 1, 2$ for baseline and the two follow-ups ($F=1$ for both), and Z is the vector for all other covariates and Y_t is the outcome score measured at time t . We will specify CG distress (K10 score) and CG work functioning (C-WLQ score), respectively, as dependent variables to test Hyp 1a and 1b. The overall treatment effect (improvement from the baseline) will be measured by β_3 . For exploratory purposes, we will test for the treatment trajectory difference by expanding the mixed model to estimate TF interactions separately for each time point.

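### The primary model estimates an arm difference at a pre-randomisation baseline and forces usual-care change onto a straight line: the first wastes precision, the second can bias the treatment effect

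*Combined protocol and SAP*

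**What the plan says.** The model is in Section 16, 9.2, under Specific Aims 1 and 2:

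Y_t = β1·T + β2·Z + β3·TF + β4·t + ε

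T is 1 for SOS and 0 for usual care. The index t takes the values 0, 1, 2 for baseline and the two follow-ups, and F is 1 at both follow-ups. Baseline is a response row. "The overall treatment effect (improvement from the baseline) will be measured by" β3. Estimating the TF term separately by visit is exploratory only.

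Other parts of Section 16 bear on this:

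- **Order of events (6.1).** "Following the consent and baseline process, CGs will be randomized to either usual care or Caregiver SOS using a random number table". Under 4.3.1 B.1, after consent "the RA will complete the initial screening and, if the CG is eligible, the baseline research assessment", and assignment follows.
- **Covariates (9.2, Preliminary Analyses).** The plan includes "testing for baseline group differences in key variables (e.g., gender, age, race/ethnicity, job flexibility, K10 and C-WLQ scores, and CR condition"), and adds a variable to the adjusted models only if a difference is found.
- **Power (9.1).** 300 caregivers, 20% attrition (120 per group), a "typical correlation of .70 between baseline and each of two follow-ups", 5% tests and 80% power give a minimum detectable effect size (MDES) of 0.235 SD. The K10 SD is about 10, and 3 points is the clinically meaningful difference.

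**The concern.** Two features of the formula matter, and they do different things.

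**Free arm term at baseline.** Randomisation follows the baseline assessment, so any arm difference in baseline K10 is chance. The model estimates it anyway, and the noise passes into β3. A chance imbalance of 1 K10 point moves β3 by about 0.24 points the other way in the printed formula, and by 0.30 with categorical time. The conditional covariate rule does not help while baseline remains a response row.

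**Linear time.** F appears only inside TF, so only the SOS arm may step at follow-up. Usual care must follow a straight line across the three visits. If both arms fall early and then level off, the line cannot fit, and part of the shared fall goes into β3.

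The documents make that shape plausible. Entry requires that the "CG screens positive for at least mild-moderate distress" (7.1), and the screen comes just before baseline, so some regression to the mean is expected. Usual care receives its contact once (4.3.1 B.3: "CGs in this arm will be contacted telephonically once by a CM"), and under 4.3.1 C.1 "participation in the SOS intervention will occur over the span of 3-4 months". Both are therefore largely complete by the 4-month visit.

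At stake are the primary and secondary estimates, their tests, and the confidence intervals that the plan will read against clinically meaningful differences.

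**Working it through.** **Inputs.** From 9.1: 150 baselines and 120 followed per arm, correlation .70 between baseline and each follow-up, K10 SD 10. Assumed: two-sided 5%; correlation ρ between the two follow-ups of .70, range .6 to .8 (not stated in the plan); an intercept within Z (none is printed); covariance treated as known. MDES = (1.960 + 0.842) × SE, in SD units.

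**1. The plan's own 0.235.** With categorical time (or an F main effect) and a free baseline, the mean of the two follow-ups has variance (1 + ρ)/2 = 0.85. Given baseline, this is 0.85 - 0.70² = 0.36. Then

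Var(β3) = 2 × [0.36/120 + (1 - 0.70)²/150] = 2 × (0.0030 + 0.0006) = 0.0072

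so SE = 0.0849 and MDES = 0.238, close to 0.235. Generalised least squares (GLS) on the printed formula, with rows (1, T, TF, t), gives SE 0.0761 and MDES 0.213. The stated MDES fits unrestricted time, not the printed linear term.

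**2. Cost of the free baseline term.** With one common baseline mean the second term drops out: Var(β3) = 2 × 0.36/120 = 0.0060, SE 0.0775.

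- Variance cut: 1 - 0.0060/0.0072 = 16.7% (18.8% at ρ = .6, 14.9% at ρ = .8).
- MDES: 0.238 to 0.217 SD, which is 2.4 to 2.2 K10 points, or 1.05 to 0.95 on C-WLQ at its stated SD of 4.4.
- Power for 3 points: 94% to 97%.
- With all correlations .8 the cut is 11%; with all .5 it is 29%.
- Within the printed linear formula, dropping β1·T alone moves SE from 0.0761 to 0.0707, a cut of 13.9% (11.5% to 16.5%).

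**3. Bias from linear time.** Let both arms change by a at 4 months and b at 9 months, with no true effect. Projecting these means onto the printed model gives bias in β3 ≈ 0.78 × (a - b/2) at ρ = .70. For a fall complete by 4 months (a = b; sizes assumed):

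| Shared fall (K10 points) | Bias in β3 | Bias/SE (SE = 0.761 points) | Two-sided false-positive rate |
|---|---|---|---|
| 1 | -0.39 | -0.51 | 8% |
| 2 | -0.78 | -1.03 | 18% |
| 3 | -1.17 | -1.54 | 34% |

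For the 3-point fall, ρ from .6 to .8 gives bias from -0.89 to -1.55 points and a rate from 23% to 52%. Dropping β1·T but keeping linear t still gives -1.01 points and 30%. Categorical time gives 0 and 5%. A fall occurring only after 4 months gives the same bias with opposite sign. The exploratory visit-specific TF terms keep β4·t, and in the 3-point case the 4-month term is biased by about -1.48 points.

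Simulation of 20,000 null trials with means 20, 17, 17 agrees:

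| Model | Mean β3 | Rejection rate |
|---|---|---|
| Printed formula | -1.17 | 33.3% |
| β1·T dropped, linear t kept | -1.01 | 29.6% |
| Categorical time, common baseline | 0.00 | 5.3% |

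With means 20, 18.5, 17, all three reject about 5%.

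**4. Conditional covariate rule.** In 1,500 simulated trials of the printed formula (random-intercept covariance assumed; the plan states none), adding baseline as a covariate left the spread of β3 at 0.076 and its slope on the imbalance at -0.24. The reported SE fell from 0.076 to 0.071, so it understated the real spread.

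**The case against.** The strongest reply is that β4·t may be meant as a visit-specific effect. No intercept is printed, t also indexes the outcome, and the stated MDES matches unrestricted time. On that reading the linear-time bias disappears. This is possible, but it is not what is printed: t is given numerical values beside T and F as a regressor, with one coefficient. Even on that reading the formula needs rewriting, and the free baseline term still costs 16.7% of variance.

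Second, the two harms do not add. If time is categorical, there is only the efficiency loss. If it is linear, the proposed model is no more precise than the printed one. That is right.

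Third, a free baseline term leaves a randomised comparison unbiased, the stated MDES already appears to carry its cost, and power for 3 points is 94% without the change. That also stands, so this part is about efficiency and not inadequate power.

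Fourth, the 34% depends on an assumed trajectory; the documents give none for usual care. With the same 3-point total but means 20, 18, 17, the bias is 0.78 × (-2 + 1.5) = -0.39 points and the rate 8%. That is fair, and the size of the bias cannot be known in advance. Its sign cannot be either, which is a reason not to let the primary estimate depend on it. The planned plots of means by visit would reveal a plateau but would not correct β3.

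**Conclusion.** The concern holds on the model as printed. The free baseline arm term is an avoidable loss of 14% to 17% of variance at a follow-up correlation of .70: 13.9% with linear time, 16.7% with categorical time. Linear time matters more. It biases β3 by about 0.78 × (a - b/2), which against the plan's 3-point meaningful difference is 0.39 points for a 1-point early fall and 1.17 for a 3-point one. The bias is zero only when usual-care change is linear in visit number. The fall size, its shape and the correlation between follow-ups are assumptions. The stated MDES and the printed model do not appear to describe the same analysis, and the plan should say which is intended. The model statement should be corrected before analysis.

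**What to change.** For K10 and C-WLQ, prespecify a constrained longitudinal model: time as a categorical variable, one common baseline mean (no β1·T), the treatment-by-follow-up term, and an unstructured covariance matrix. A near-equivalent is to model the 4- and 9-month scores with baseline always a covariate, although this drops caregivers who have only a baseline.

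Remove K10 and C-WLQ from the conditional covariate rule in 9.2. Restate the MDES for the chosen model and give the assumed correlation between the two follow-ups.

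This changes wording only. It stays in PROC MIXED and needs no added participants, visits or data. Against the printed formula the variance is about the same: 0.0775²/0.0761² is roughly 1.035, so 3.5% higher at ρ = .7, 5% lower at .6 and 15% higher at .8. Power for 3 points goes from 97.6% to 97.2%. Relative to that formula, the gain is removal of the linear-time bias.

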If the project does not fit into one of the above categories, it does not qualify for expedited review.

SECTION 14: ABSTRACT

1. **Objectives(s):** The objectives of this study are to, 1) determine the extent to which, relative to usual care, a novel intervention providing evidence-based, telephonic CG/work stress self-management counseling is related to changes in CG psychological distress and ability to function effectively in work and CG roles, and 2) evaluate whether participation in the intervention is related to CGs' overall wellbeing and CRs' health care utilization.
2. **Research Design:** Randomized controlled, longitudinal trial
3. **Methodology:** We will compare pre/post changes among 300 CGs allocated to the Caregiver SOS (for Self-Management of Stress) program or usual care. CGs who, 1) care for Veterans diagnosed with depression, anxiety, PTSD, and/or TBI and, 2) screen positive for clinically significant distress and CG/work role difficulty will be recruited to participate from two VA Medical Centers and their affiliated outpatient clinics. A novel intervention, Caregiver SOS includes 6, 1-hour telephonic sessions with a care manager. Usual care will consist of 1 telephonic session with a care manager. Primary and secondary outcomes will be pre-post change in CG distress and work functioning, respectively. Additional CG and CR outcomes (i.e., physical mental and interpersonal functioning) also will be measured and analyzed. CRs' VA health utilization data will be extracted from clinical patient records and non-VA health utilization data will be collected via CG self-report. Intent to treat analysis using mixed effects models will be used to test the study hypotheses. We anticipate that CGs in the intervention arm will show significantly greater improvements in outcomes compared to those in usual care.
4. **Clinical relationships:** N/A

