B.2 Caregiver SOS Intervention Procedures: SOS care is a comprehensive approach to helping CGs gain the knowledge, skills and confidence to achieve success in stress self- management. The intervention concept was developed by [name] and her research group and will be adapted for the VA context. Through a range of techniques, CGs develop abilities to modify psychological and social sources of stress, including the stress associated with performing both caregiving and work roles. SOS care is brief, telephonic care (6 one-hour sessions over 3-4 months) offered during either work or non-work hours, and tailored to the CG's needs, preferences, and priorities. Supportive visual aids and CG workbook material are distributed via mail or email. SOS is delivered by SOS-trained VA CMs; clinicians with a Master's degree or higher in Social Work or Psychology. SOS care is an opportunity for CGs to form an alliance with a VA healthcare professional ready to meet their health and psychosocial needs, including concerns about CR health and treatment.

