To yield findings that will be used to inform future research and implementation endeavors, we will run exploratory analyses (using the analytic strategy outlined above) that address Aim 2. Overall CG physical and mental well-being and CR utilization of VA and non-VA services (including CG-related services), will be modeled as dependent variables. Given that we are underpowered for a full-scale quality of care analysis, we will compare summary statistics and estimates (with confidence intervals) across groups for descriptive purposes as opposed to formal statistical hypothesis testing. We will model group differences in CR service use (using negative binomial models and chi-squares) using count data of utilization/appointments from VINCI and CG self-report surveys (which will ask about CR non-VA healthcare use and CG use of VA/non-VA support services). Service utilization will be operationalized as the number (simple count) and occurrence of any (yes/no) outpatient visits and inpatient admissions/hospitalizations, and the total number of days hospitalized/bed days. Outpatient visits will be further classified based on the visit stop code into medical or surgical, psychiatric/substance use, social work, occupational therapy, other specialty care, and ER encounters. Inpatient hospitalizations will be further classified based on the primary diagnosis for admission into medical or psychiatric/substance use hospitalizations. For each participant, all utilization data will be summed and compared over two intervals (1 year pre-baseline and 1 year post-4 month assessment). Inpatient and outpatient utilization will be analyzed separately. We will also carefully examine specific domains of utilization where we expect to see an effect, such as MH, social work, and occupational health visits. While the differences may not be statistically significant, even clinically meaningful increases in service use by the Veteran and CG would be consistent with the VA mission of improving access to care.

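### The exploratory utilization outcome has two unreconciled time windows, one anchored differently by arm, and its survey-only items cannot cover the stated post-year

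*Combined protocol and SAP*

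**What the plan says.** All places are in the combined protocol and SAP.

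- **Analysis window.** Section 16, 9.2 (Specific Aims 1 and 2) adds up all of a participant's utilization and has it "compared over two intervals (1 year pre-baseline and 1 year post-4 month assessment". It names two sources, VINCI counts and caregiver surveys. The surveys ask about the care recipient's non-VA care and the caregiver's own use of support services.
- **Database window.** Section 16, 8.1 (Data Collection Technology and Tools) describes a time-window "variable spanning one year prior to and one year following the final CM call". It does not say what the variable is for.
- **Care manager calls.** Section 16, 4.3.1 B.2 describes SOS as "brief, telephonic care (6 one-hour sessions over 3-4 months". For UC, B.3 says "CGs in this arm will be contacted telephonically once by a CM", after which contact is for research assessments only. Section 16, 4.3.2 lets participants stop sessions whenever they wish.
- **Surveys.** Section 16, 4.3.1 B.1: "All CGs will be contacted again for 4- and 9-month follow-ups". No later survey is planned.
- **Data source.** The Section 14 abstract says "non-VA health utilization data will be collected via CG self-report", and 9.2 says "While non-VA care will be assessed by self-report, VA claims databases are complete by design". Section 8.1 says that VA and non-VA use together "will be obtained using VINCI or by self- report".

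**The concern.** Two analysts working from 8.1 and 9.2 would build different datasets. The 8.1 anchor is also a poor one for a randomised comparison. It occurs after randomisation, the number of calls that determines it differs by arm, and within SOS it moves earlier when a caregiver stops early. A pre-period counted back from that call would not be a true pre-treatment period in SOS.

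The second problem remains even if 9.2 governs. Its post-year runs well past the last survey, yet it asks for every item to be summed over that year. For items known only from the surveys this cannot be done. A raw sum would set a short post-period against a nominal year before baseline and understate any rise in service use. Hyp. 2b expects a rise, and caregiver-related services are one of the things it names.

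**Working it through.** The documents give no sample size or power figure for Hyp. 2b, so there is no stated figure to reproduce. The check is timeline arithmetic in months from baseline.

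**Inputs**

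- 9.2 intervals: -12 to 0, and 4 to 4 + 12 = 16.
- 8.1 window for a final call at month c: c - 12 to c, and c to c + 12.
- SOS final call: six sessions over 3-4 months (B.2). The start date is not stated. If sessions start at about baseline (assumption), c = 3 to 4 for those who complete.
- UC call: one call (B.3), date not stated. Assumed c = 0 to 1.
- Last survey: month 9 (B.1).

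**Step 1. Can the 8.1 window feed the 9.2 comparison?**

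The 9.2 intervals run 16 - (-12) = 28 months end to end. The 8.1 span is 12 + 12 = 24 months. To reach month -12 requires c - 12 ≤ -12, so c ≤ 0. To reach month 16 requires c + 12 ≥ 16, so c ≥ 4. No value of c meets both conditions, in either arm.

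**Step 2. Where does the 8.1 window fall in each arm?**

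| Arm | c | Pre-year | Post-year | Pre-year months after baseline | Post-year months shared with 9.2 |
|---|---|---|---|---|---|
| SOS | 3 | -9 to 3 | 3 to 15 | 3 | 11 of 12 |
| SOS | 4 | -8 to 4 | 4 to 16 | 4 | 12 of 12 |
| UC | 0 | -12 to 0 | 0 to 12 | 0 | 8 of 12 |
| UC | 1 | -11 to 1 | 1 to 13 | 1 | 9 of 12 |

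Every row has 12 months before and 12 after, so observation length is equal. What differs is calendar placement and how much of the pre-year follows baseline. If both arms start after the same lag, the anchors are 3-4 months apart and the SOS pre-year holds 3-4 months of sessions, whatever the lag. Across the assumed ranges in the table the anchors are 2-4 months apart. An SOS caregiver who stops early has a smaller c.

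**Step 3. How much of the 9.2 post-year can the surveys reach?**

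- Reachable: 9 - 4 = 5 months; 5/12 = 42%.
- Not reachable: 16 - 9 = 7 months; 7/12 = 58%.

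This is an upper limit on coverage. Appendix 1, which holds the assessment details, is not in the supplied copy, but no recall period used at month 9 can reach months 9 to 16. With steady use, complete reporting of months 4 to 9 and a fully reported pre-year (assumptions), the post count would be 5/12 of the pre count with no real change. The survey schedule is the same in both arms, so the shortfall is too.

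**The case against.** The best defence is that 9.2 is the analysis section, states its intervals outright and times them alike in both arms. Section 8.1 says only that the database will carry a window variable, not that extraction stops there. If 9.2 governs and VINCI is extracted in full, VINCI counts are comparable between arms. That stands. It does not remove the contradiction, because a variable with the 8.1 definition cannot mark out the 9.2 intervals.

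Appendix 4, the data analysis plan, is also absent from the supplied copy and might settle the window. The point is therefore limited to the supplied text.

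On data sources, the wording in 8.1 covers VA and non-VA care together and can be read consistently with the abstract and 9.2. The survey limit is accordingly claimed for caregiver support-service use, and for the care recipient's non-VA care where it is self-reported.

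Three stronger readings are tempting and not supported:

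- **SOS would be observed for longer after treatment, inflating its counts.** This needs the 8.1 span to cut off the data and the 9.2 intervals then to be applied to what is left. No section says so. Either window used alone gives 12 months per period in each arm.
- **The survey gap favours one arm.** By design it is the same length in both.
- **Month 16 for late enrollees contradicts the planned data-collection period.** The period in 4.3.1 C.1 covers screening, baseline, intervention and the two follow-up assessments. It does not date the VINCI extraction.

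**Conclusion.** The point holds, as a minor one. On the supplied text, 8.1 and 9.2 define different windows for the same outcome, and the 8.1 window cannot supply the 9.2 comparison (24 months against 28). If the 8.1 anchor defined the comparison, observation length would be equal, but the SOS pre-year would include about 3-4 months of intervention for caregivers who complete the sessions, and the calendar periods would differ by arm. The exact shift depends on start and call dates that are not stated.

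Under 9.2, survey-only items can cover at most 5 of 12 post months. This lowers post-period counts and the pre/post change in both arms alike and does not in itself bias the comparison between arms. The consequences stay within an aim that the plan calls exploratory and underpowered and analyses descriptively. Aim 1 is unaffected.

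**What to change.** 1. In Section 16, 8.1, replace the final-call anchor with the 9.2 window, timed from baseline or randomisation in both arms: months -12 to 0 and months 4 to 16, using the scheduled month-4 date rather than the date the assessment took place. Extract VINCI over that whole span for every participant.
2. In Section 16, 9.2, exempt survey-only items from the sum over months 4 to 16. List them, and analyse them separately over a stated interval that ends no later than month 9 and is equal in both arms.

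The cost is two or three sentences and the extraction code, with no new data collection. There are two drawbacks. VINCI and self-report results would cover different periods and could not be added together. VINCI extraction must also wait until the last enrollee reaches month 16, which 9.2 already implies. The start of the self-report interval should be set from the recall periods in the survey instruments.
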